6.4 REPORTING PROCEDURES FOR ADVERSE EVENTS

6.4.1 Recording Adverse Events

The Investigator will record all AEs (both AEs and SAEs) considered attributable (relationship of possible, probable, causal relationship) to the study procedure or either of the HARMONIC 1100 Shears or GEN11 devices in the source documents and eCRF.

Standard medical terminology should be used when recording AEs. In addition, the following information should be recorded:

- Onset date:
- Resolution date or date of death;
- Severity of the event;
- Indication of whether the event is serious;
- Relationship of AE to the study devices;
- Relationship of AE to the study procedure;
- Action taken:
- Event status; and
- Was AE anticipated or not (only for SAEs).

Data related to AEs will be collected until the event resolution, or until the event is considered stable, or until all attempts to determine the resolution of the event are exhausted. All AEs that are unresolved at study completion (or at the last visit completed for early withdrawal subjects) will be recorded as ongoing at study end.

6.4.2 Reporting Adverse Events

The Investigator is required to report AEs to the Sponsor within 2 weeks from when the study site becomes aware of the event. All AEs must be reported on the AE eCRF and be documented in a timely manner throughout the study duration, with reporting of AEs starting from the time the subject is enrolled.

6.4.3 Reporting Serious Adverse Events

Any AE that the Investigator determines to be a SAE must be reported by the study site

within 72 hours of becoming aware of the event to the Sponsor by completing the AE eCRF. A notification containing the pertinent data will be automatically generated by the EDC system and forwarded to the Sponsor. If applicable, supporting SAE documentation should be de-identified and provided to the Clinical Trial Leader. The report of an SAE by a study site does not constitute an admission that study personnel or the user facility (hospital/clinic) caused or contributed to the event. The study site is also responsible for submitting SAEs to the reviewing IRB/EC per their IRB/EC procedures.

7.0 PRODUCT COMPLAINTS

A product complaint is any written, electronic, or oral communication that alleges deficiencies related to the identity, labeling, quality, durability, reliability, safety, effectiveness, or performance of a device after it is released for distribution. A product complaint may or may not be associated with an AE/SAE.

7.1 REPORTING PRODUCT COMPLAINTS FOR MARKETED DEVICES

7.1.1 Reporting of Approved EES Marketed Devices

All product complaints related to devices in the procedure shall be documented throughout the clinical investigation. Product complaints related to Ethicon-manufactured HARMONIC 1100 Shears or GEN11 devices must be reported to the Sponsor in a timely manner and no later than 24 hours after becoming aware of the event. When a sponsor representative becomes aware of a product complaint, the Product Complaint Team must be notified within 24 hours after becoming aware of the event. The Product Complaint Form must be emailed to the Sponsor Customer Complaint team at the following email address:

[contact]

The sites will report Product Complaints by completing the Product Complaint Form. If a product complaint is related to a safety event, the site must complete an AE eCRF as well. One copy of the processed form should be kept on-site, and the device should be retained. Sponsor representatives will organize collection of the device for evaluation as needed.

7.1.2 Reporting of Approved Marketed Devices and Commercially Available Devices (not Ethicon)

The site should report Product Complaints of non-Ethicon devices that are approved marketed devices or commercially available medical devices according to the specific product's manufacturer specifications/guidelines.

	8.10 Assessment of Site Homogeneity	13
9	Data Monitoring Committee (DMC)	13
	Appendix: Table Shells and List of Listings to be Generated	14

1 Introduction

This is the Statistical Analysis Plan (SAP) for the final analysis of data collected under Protocol ENG_2020_06 (Amendment 3, dated May 17, 2023). This SAP describes in detail the statistical methodology and statistical analyses for this protocol.

1.1 Study Objectives

The primary objective of this study is to demonstrate the acceptable performance and safety of the HARMONIC 1100 Shears and GEN11 devices when used per the instructions for use (IFU) in pediatric surgical procedures (general) or adult surgical procedures (general, gynecological, urological, and thoracic) where at least one single vessel is planned to be transected by the HARMONIC 1100 Shears.

The secondary objective of this study is to demonstrate the acceptable performance and safety of the HARMONIC 1100 Shears in the transection of > 5 to 7 mm diameter size vessels.

1.2 Study Design

This prospective, single-arm, multi-center study will collect clinical data in a post-market setting for the pediatric population (general surgical procedures) and adult population (general, gynecological, urological, and thoracic surgical procedures). Investigators will perform each procedure using the device in compliance with their standard surgical approach and the HARMONIC 1100 Shears and GEN11 IFUs.

Subjects will be consented and screened anytime during a period of 8 weeks prior to the date of surgery. Subjects will be considered enrolled when the HARMONIC 1100 Shears has been attempted to be used for at least one single vessel transection during pediatric surgical procedures (general) and adult surgical procedures (general, gynecological, urological, and thoracic). All subjects enrolled will be followed post-operatively through discharge and again at 28 days (\pm 14 days) post-surgery; therefore, from the surgery date to study exit, the duration will be approximately 6 weeks.

A minimum of 165 subjects enrolled (maximum of 328 subjects enrolled) will be included in the study from up to 15 surgery centers globally with the following procedure targets:

- A minimum of 33 subjects enrolled to a maximum of 40 subjects enrolled for Pediatric general procedure;
- A minimum of 33 subjects enrolled to a maximum of 119 subjects enrolled for Adults general procedures (Adult HPB, Adult lower GI and Adults gastric {gastrectomy [e.g., subtotal, total], esophagectomy, RYGB, sleeve gastrectomy, or BPD/DS});
- A minimum of 33 subjects enrolled to a maximum of 40 subjects enrolled for Adult gynecological (e.g., hysterectomy, oophorectomy, myomectomy or endometriosis resection);

- A minimum of 33 subjects enrolled to a maximum of 40 subjects enrolled for Adult urological (e.g., nephrectomy, cystectomy or prostatectomy); and
- A minimum of 33 subjects enrolled to a maximum of 89 subjects enrolled for Adult thoracic (lung resection [branches, excluding main pulmonary artery {PA}/pulmonary vein {PA}]).

2 Treatment Assignment

This is a single-arm study where all enrolled subjects will have the HARMONIC 1100 Shears device utilized for transection of at least one vessel.

3 Randomization and Blinding Procedures

As this is a single-arm study, no randomization will occur, and no blinding procedures are required.

4 Interval Windows

Interval windows for the purpose of analysis in this study will not be defined outside of those already specified in the protocol for visit scheduling as the collection of data for the primary and secondary performance endpoints occurs intra-operatively. The final visit occurs approximately 4 weeks after surgery, thus no interval windows need to be defined given the absence of long-term follow-up in this study. The Schedule of Events specifies a window of 14 days around the scheduling of the 4-week follow-up visit, and any information entered in the eCRFs at this visit will correspond to the 4-week visit. There will be no assigning of observations to time points outside of the visit to which they are recorded in the eCRFs.

5 Levels of Significance

The hypotheses in this study will be evaluated using a one-sided significance level of 0.025. Estimation of all additional endpoints will be performed using two-sided 95% confidence intervals.

6 Analysis Sets

All Enrolled Set (AES): The all enrollment set contains all subjects who provide informed consent for this study . The AES will be used for subject disposition and all listings.

Full Analysis Set (FAS): The FAS will includeds all subjects in whom the HARMONIC 1100 Shears is utilized during the surgical procedure to transect at least one vessel and have assessment for the primary endpoint. The summary of all primary and secondary performance and safety endpoints will be performed by surgical population (pediatric and adult), surgical procedure group, procedure subgroup, and on the entire pooled set of subjects. The hypotheses described in Section 8.4.1 below will be evaluated on the pooled set of subjects and the > 5 to 7

mm diameter vessel population. The > 5 to 7 mm diameter vessel population will be based off the surgeon determination of the vessel size.

Safety Analysis Set (SAS): The SAS will include all subjects who signed informed consent and for whom HARMONIC 1100 Shears device is utilized during the surgical procedure. The safety endpoints will be summarized using SAS by surgical population (pediatric and adult), surgical procedure group, procedure subgroup, and on the entire pooled set of subjects.

7 Sample Size Justification

Primary performance analysis: A sample size of at least 165 subjects is required to have a minimum of 80% power for rejecting the null hypothesis that the rate of Grade 3 or lower transections is less than or equal to 87.5% when the expected rate of Grade 3 hemostatic transection is at least 94.0% using exact binomial test and a one-sided significance level of 0.025. This sample size estimation makes the assumption of one transection per subject which is likely very conservative as most subjects may have 2 or more transections during their procedure. Therefore, it is expected that greater than 165 transections will be observed and thus the study will be well powered for evaluating the performance goal hypothesis under the assumption of independence of observations. At the time of the study protocol amendment 3, it was found that on average there were 2 vessel transections per subject.

The assumption of independence and its impact on the overall study conclusion will be evaluated through sensitivity analyses. Given that the primary endpoint is being evaluated intra-operatively, it is not anticipated that there will be subject dropout prior to evaluating this endpoint, thus no adjustment or increase in subject enrollment is planned to account for dropout. A minimum of 33 subjects will be enrolled into each of the five individual procedure subgroups.

The performance goal of 87.5% was selected to represent a minimum acceptable level of clinical performance across all procedure groups. A recent energy study¹ with the same hemostasis endpoint in similar procedure groups showed point estimates of the primary endpoint ranging from 94.2% to 100.0%. The 95% confidence interval for the lowest performing group had a lower bound of 89.3%, thus selection of 87.5% represents a less than 2% region of indifference for maintaining average acceptable performance. In the recent study, average performance across all groups was 96.2% and selection of 87.5% as the performance goal corresponds to a noninferiority margin of 8.7% which is less than the commonly chosen value of 10%. Finally, consideration of the performance goal of 87.5% in the context of the relative reduction from the overall average performance of 96.2%, this can be interpreted as preserving at least 91.0% of the original average treatment effect ($87.5/96.2 * 100\% = 91.0\%$). Maintaining at least 91.0% of the expected effect of similar therapies represents a clinically meaningful metric for maintaining minimum acceptable performance and is actually considerably larger than the standard limits used for bioequivalence where the lower bound for relative therapeutic efficacy is set at 80%,

considerably lower than the 91.0% of therapeutic efficacy that is represented by a performance goal of 87.5% chosen for this trial.

Secondary performance analysis (Vessel size > 5 to 7 mm): The hypothesis and evaluation of the hypothesis for the secondary performance endpoint will be similar to the primary performance endpoint. Therefore, a sample size of at least 165 vessels is required to have a minimum of 80% power for rejecting the null hypothesis. The number of vessels transected with a diameter size of > 5-7 mm will be continuously checked throughout the course of the study to achieve the required number of vessels.

Safety Analysis: From a safety perspective on the pooled analysis of 165 subjects and in consideration of rare AEs that may occur (e.g., bleeding requiring blood product transfusion), for an event that has an incidence rate of, for example, 1%, then in a sample of 165 subjects, the probability of observing at least 1 event is 81.0% under a binomial probability model. Thus, this sample size provides a high probability of observing rare events if they do occur, and provides reasonable assurance to conclude that the likelihood of such AEs is less than 2.3% if they do not occur based on the upper limit of an exact 95% confidence interval when 0 events out of 165 subjects are observed.

8 Analyses to be Conducted

8.1 General Conventions

Subject data will be summarized in tables and further details will be provided in listing. All eCRF data will be listed per subject for all subjects. Descriptive statistical analyses will be provided for pre-specified variables. Categorical variables will be summarized descriptively by frequencies and associated percentages. Continuous variables will be summarized descriptively by number of subjects, mean, standard deviation, median, minimum, and maximum.

Data recorded at the nominal visits will be presented in summary tables; however, unscheduled visits will not be included in summary tables. Listings will include both scheduled and unscheduled visits.

Analyses will be conducted using SAS software. During the course of programming of tables that are mocked up in this SAP, minor modifications may become necessary. Examples of these minor modifications include, but are not limited to, re-wording of a footnote, addition of a footnote, re-labeling of a column, or addition or removal of a column from a table or listing. In cases where modifications to tables or listings are not related to a change in statistical analysis methodology or conclusions that could be made on the originally proposed methodology, then no amendment of the SAP is necessary. Any final analyses that differ from what has been specified in this document will be identified within the final statistical output and documented within the clinical study report.

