3.5 SCHEDULE OF EVENTS

Table 2: Schedule of Events

	Visit 1 ^a	Visit 2ª	Visit 3	
Activity	Screening Visit (Day -56 to Day 0)	Procedure Day (0) Through Discharge Visit	Post Procedure Follow Up Visit (Day 28 ± 14) ^b	Unscheduled Visit, if applicable ^b
Informed consent/assent, as applicable	X			
Demographics (age, gender, race, and ethnicity)	X			
Administer pregnancy test as per standard of care	Х	x		
Height and weight (both with no shoes)		X		
Medical and surgical history (including diagnosis)	Х	х		
Review of inclusion/exclusion criteria	X	X		
Concomitant medications	Х	X	Х	Х
Surgical data collected for evaluation		X		
Collect vessel image ^c		X		
Collect generator questionnaired		X		
Collect surgeon questionnairee		X		
Concomitant procedures conducted besides primary procedure		×		
Re-operation(s) associated with the primary procedure			Х	Х
Assess for device-related and procedure-related AEs		х	Х	Х
Subject completion/discontinuation		X	Χ	X

a. Visit 1 and Visit 2 may be combined;

AE = adverse events.

b. This can be either an office visit or telephone follow-up;

c. The image captured where the vessel is below the open jaw of the HARMONIC 1100 Shears perpendicular to the vessel during the primary procedure at Visit 2;

d. The generator questionnaire will be completed after each Visit 2 procedure;

e. The surgeon questionnaire will be completed after the investigator has completed his/her second procedure in any of the seven procedure groups.

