3.6.4 Unscheduled Visit(s)

Any unscheduled visit between Visit 2 and Visit 3 will be documented including the reason for the visit. This visit can be either an office visit or a telephone follow-up. Data to be collected is listed in Section 3.5.

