8.5 Safety Analyses

The primary safety endpoint in this study is the occurrence of device-related AEs. As per the study protocol, device-related AEs are those identified as having a relationship of possibly, probably, or causally. AEs unrelated to the study device are recorded as 'not related' on the CRF. Both device-related and procedure-related AEs reported during the study will be coded to MedDRA. All reported AEs will be summarized by MedDRA system organ class and preferred term by surgical population (pediatric and adult), surgical procedure group, procedure subgroup, and in total. Separate summaries will be provided for device-related and procedure-related AEs. Serious AEs will be summarized in a similar manner. In addition, these analyses will also be completed for the vessels in the > 5 to 7 mm diameter size vessel range.

Safety endpoints are as follows:

- All AEs
- All Serious AEs
- All AEs related to the study device
- Serious AEs related to the study device
- All AEs related to the study procedure
- Serious AEs related to the study procedure

Additional key safety outcomes identified in the CER #SCN070380 (ref. Table 40) that includes the bleeding/hemorrhaging and infection (including abscess) will be presented by surgical population (pediatric and adult), surgical procedure group, procedure subgroup, and in total. The observed event rates for these key safety outcomes from the current study will be presented along with the median and range event rates from the CER for descriptive comparison with no statistical test performed.

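### Could the unscheduled-visit rule, or the mention of safety under two analysis sets, drop adverse events from the SAP's safety tables?

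*SAP*

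**What the plan says.** SAP section 8.1 sets a general convention for tables: "Data recorded at the nominal visits will be presented in summary tables; however, unscheduled visits will not be included in summary tables". Listings carry both kinds of visit. SAP section 8.5 makes the occurrence of device-related AEs the primary safety endpoint and adds: "All reported AEs will be summarized by MedDRA system organ class and preferred term by surgical population". It sets no visit limit and names no analysis set.

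In the protocol's Table 2 (section 3.5), the row "Assess for device-related and procedure-related AEs" is marked for Visit 2, Visit 3 and the unscheduled visit. Section 3.6.4 adds: "Any unscheduled visit between Visit 2 and Visit 3 will be documented including the reason for the visit". On recording, section 6.4.1 says: "The Investigator will record all AEs (both AEs and SAEs) considered attributable" to the procedure or the devices, and lists what is entered for each event. Section 6.4.2 requires the AE eCRF.

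SAP section 6 admits to the FAS subjects in whom the device is used "to transect at least one vessel and have assessment for the primary endpoint". The same paragraph continues: "The summary of all primary and secondary performance and safety endpoints will be performed by surgical population". The next paragraph reads: "The SAS will include all subjects who signed informed consent and for whom HARMONIC 1100 Shears device is utilized during the surgical procedure", and it directs that the safety endpoints be summarized on that set. Protocol section 5.6 has one set for performance and safety (at least one vessel transected). The protocol synopsis asks only that the device be utilized.

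**The concern.** There were two worries, both about the primary safety endpoint.

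First, an AE that comes to light between discharge and the 28-day visit may well be found at an unscheduled visit. A programmer who applied section 8.1 without exception would list that event but not tabulate it, and the tabulated AE rate would be too low.

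Second, safety appears under two sets with different entry conditions. Enrollment needs only an attempted transection (protocol section 3.1), and missing data are not imputed (SAP section 8.7). A subject with no completed or no graded transection would be in the Safety Analysis Set but not in the FAS. Such a subject could plausibly have a device-related AE, and with rare events one subject can decide whether a table shows none or some.

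**Working it through.** **The plan's own safety figures.** Inputs from SAP section 7: n = 165, event rate 1%.
- Chance of at least one event: 1 − 0.99^165 = 0.8095. Stated: 81.0%.
- Exact two-sided 95% upper limit at 0/165: 1 − 0.025^(1/165) = 2.21%. Stated: below 2.3%.

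The first figure reproduces and the second is consistent.

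**Unscheduled visits.** Table 2 marks four items for these visits.

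| Item | What the SAP does with it |
|---|---|
| Concomitant medications | Listing only (8.3) |
| Re-operations | No table named |
| AEs | All reported AEs summarized (8.5) |
| Completion/discontinuation | Tabulated per subject (8.2) |

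Section 8.1 concerns data that belong to a visit. The AE items in protocol section 6.4.1 are onset and resolution dates, severity, seriousness, relationship, action and status. None of them is a visit. AEs are therefore event records, and section 8.5 is the specific rule for them. Unscheduled visits fall between Visits 2 and 3, and AEs are assessed again at Visit 3, so a later scheduled contact also covers them. The same reasoning applies to discontinuations under section 8.2.

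For scale only, suppose section 8.1 did override 8.5, and a share f of subjects with the event had it recorded only at an unscheduled visit. The documents give no f. The chance that a 1% event reaches a table is 1 − (1 − 0.01(1 − f))^165, which is 77.5%, 71.1% and 56.3% for f = 10%, 25% and 50%. A literal override would matter, but it is not what the plan directs for AEs.

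**Analysis sets.**

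| Set | Entry conditions | What is said about safety |
|---|---|---|
| FAS | Vessel transected and primary endpoint assessed | Names the breakdowns; does not say safety is analyzed on the FAS |
| Safety Analysis Set | Consent and device use | Directs that safety be summarized on this set |

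The FAS sentence closely follows protocol section 5.6, where one set served both purposes. It looks like text carried over when the SAP split that set in two.

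The FAS lies inside the Safety Analysis Set. A completed transection with failed hemostasis is Grade 4, which is an assessment, so that subject stays in the FAS. Only an uncompleted or ungraded transection separates the sets. Protocol section 5.2 and SAP section 2 expect at least one vessel transected in every enrolled subject, section 3.4.2 has each transected vessel graded, and SAP section 7 expects no dropout before that assessment.

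**Smallest non-zero case.** Assume exactly one treated subject has no graded transection and also has the only device-related AE (exact 95% intervals).

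| Enrolled | FAS | Safety Analysis Set |
|---|---|---|
| 165 | 0/164: 0% (0 to 2.22%) | 1/165: 0.61% (0.02% to 3.33%) |
| 328 | 0/327: 0% (0 to 1.12%) | 1/328: 0.30% (0.01% to 1.69%) |

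If k of 165 subjects were ungraded and the FAS were used, the 81.0% would become 80.8%, 80.0% or 78.9% for k = 1, 5 or 10. The zero-event upper limit would become 2.22%, 2.28% or 2.35%.

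**The case for a change.** The best case for a change is that the wording does conflict, on the primary safety endpoint, and could be cured in a few words. The unscheduled-visit rule has little to act on besides AEs and discontinuations. SAP section 4 forbids moving an observation to another visit, so such data cannot be reassigned to Visit 3. Section 8.5 names no analysis set, and the protocol's synopsis and section 5.6 differ from each other. Vessels transected in a concomitant procedure do not count toward the primary endpoint (protocol section 3.4.2), which is a further way for a treated subject to miss the FAS. Settling the denominator before tables are run avoids a choice made with the data in view.

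The textual points stand: section 8.1 is unqualified and the reference to safety in the FAS paragraph is stray. The inference that events would be lost does not stand. Tabulating an event-level record whatever its visit does not reassign it to another visit, so section 4 is no obstacle. The choice of denominator is not open either, because one paragraph, and only one, says which set the safety endpoints are summarized on.

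**Conclusion.** No change is needed. This is a clerical looseness that analysts resolve in one sensible way: all reported AEs, tabulated on the Safety Analysis Set. That is what the SAP's specific clauses already direct.

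No stated figure is wrong, and the safety endpoint carries no hypothesis test. The number of affected events or subjects cannot be derived from the documents and may be zero, in which case the tables are identical under either reading. The one-subject contrast, 0/164 against 1/165, is a constructed case. An AE left out of a table would still appear in the listings, and section 8.1 requires departures from the planned analyses to be documented in the study report.

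The conclusion rests on two assumptions: that the AE form is organized by event, as the items in protocol section 6.4.1 indicate, and that the table shells, which are in a separate document not seen here, follow section 8.5 and the Safety Analysis Set paragraph.
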